7. INVESTIGATIONAL PLAN

7.1. Overall Study Design

This Phase 4, randomized, double-blind, placebo-controlled study will evaluate the PK and safety of OCA treatment in patients with PBC and moderate to severe hepatic impairment defined as CP-B and CP-C including a broad distribution of MELD scores (ranging from 6 to 24). Approximately 50 patients (including at least 20% of patients with CP-C) will be enrolled in the study. Patients will be screened ≥ 14 days but not more than 28 days prior to entering the study (Day 1). Patients who meet all eligibility requirements will be randomized in a 1:1 ratio to 1 of 2 treatment groups: Placebo or OCA. Randomization will be stratified by CP class. Baseline MELD scores will be monitored on an ongoing basis to ensure adequate distribution of MELD scores.

[figure not shown]
Following completion of safety assessments and laboratory specimen collection, blinded investigational product will be dispensed with instruction to begin dosing the same day (Day 1) at OCA 5 mg or placebo once weekly.

Double-Blind Treatment Period: During the 48-week treatment period, an initial safety visit will occur at Week 3. After the Week 6 Visit, subsequent clinic visits will occur approximately every 6 weeks for the assessment of safety, tolerability, PK, and PD. Titration may be considered as early as the Week 12 Visit (see [Section 7.3](#)). Fasting PK assessments will be performed in all patients participating in the study on Day 1, Week 6, and Week 36. Serial PK sampling (which also includes a fasted PK assessment) will be performed at Week 12, 18, 24, 30, and 48.

Patients who have completed their 48-week, double-blind treatment period will continue double-blind treatment until all randomized patients have completed their 48-week treatment period and the database for that period is locked. An open-label extension study in which all patients receive OCA will be considered following review of blinded safety and PK data.

7.1.1. Study Design Diagram

Figure 1: Study Design

OCA = obeticholic acid, PBC = primary biliary cholangitis

Notes: Initial dose titration of investigational product may be considered as early as the Week 12 Visit, or any study visit thereafter for patients on all dosing regimens, based on tolerability and safety laboratory tests from the previous visit. Subsequent dose titration(s) may occur no earlier than 6 weeks after the previous dose titration and will be based on tolerability.

Patients who complete Week 48 will continue double-blind treatment until all randomized patients have completed their participation in the 48-week treatment period and the database for that period is locked.

7.1.2. Schedule of Study Procedures

Table 1: Schedule of Study Procedures

			Double-Blind Treatment Period (Weeks) ^b									Double-Blind Extension
	Screening	Day 1 ^a	3 ^c	6 ^d	12	18	24	30	36	42 ^c	48/ ET/ EOS/EOT	Every 3 months
Visit Window (+/-)	-28 to -14 days		±1 wk	±1 wk	±1 wk	±1 wk	±1 wk	±1 wk	±1 wk	±1 wk	±1 wk	±2 wks
Fast ≥8 h Prior to Visit ^e	X	X	X	X	X	X	X	X	X	X	X	X
Informed Consent	X											
Medical/PBC History	X											
Inclusion/Exclusion Criteria	X	X										
Physical Exam ^f	X	X		X	X	X	X	X	X		X	X
Vital Signs and Weight	X	X		X	X	X	X	X	X		X	X
Medical and Surgical Procedures		X	X	X	X	X	X	X	X	X	X	X
Adverse Events	X	X	X	X	X	X	X	X	X	X	X	X
Prior and Concomitant Medications	X	X	X	X	X	X	X	X	X	X	X	X
Assessments for Child-Pugh Score ^g	X	X		X	X	X	X	X	X		X	X
Patient Questionnaires (Pruritus VAS, PBC-40, EQ- 5D-5L, and CLDQ) ^h		X		X	X	X	X	X	X		X	X
Randomization/Treatment Assigned		X										
Dispense IP ⁱ		X			X	X	X	X	X	X	X	X
Dose Titration Assessment ^j					X	X	X	X	X	X	X	X
IP Accountability/ Compliance			X	X	X	X	X	X	X	X	X	X

Table 1: Schedule of Study Procedures (Continued)

			Double-Blind Treatment Period (Weeks) ^b									Double-Blind Extension
	Screening	Day 1 ^a	3 ^c	6 ^d	12	18	24	30	36	42 ^c	48/ ET/ EOS/EOT	Every 3 months
Visit Window (+/-)	-28 to -14 days		±1 wk	±1 wk	±1 wk	±1 wk	±1 wk	±1 wk	±1 wk	±1 wk	±1 wk	±2 wks
Urinalysis	X	X									X	X ^p
Urine-based β-hCG Pregnancy Test ^k	X	X		X	X	X	X	X	X		X	X
Virology (HCV/HBsAg)	X											
Serum Chemistry/Hematology/Coagulation ^l	X	X	X	X	X	X	X	X	X	X	X	X
Amylase and Lipase	Sample to be collected if the patient experiences acute pancreatitis or cholecystitis.											
PK Fasting Collection		X		X					X			
PK Serial Collection ^m					X	X	X	X			X	
PD Markers: Bile Acid/C4/FGF-19		X		X	X	X	X	X	X		X	
TE/ELF (HA, P3NP, and TIMP-1) ⁿ		X			X		X		X		X	X ^o
12-Lead Electrocardiogram	X										X	X ^p
Hepatic Ultrasound ^q	X ^r	X ^s					X				X	X ^o
Gallbladder assessment (ultrasound)	X ^r	X ^s										

AE = adverse event; eCRF = electronic case report form; C4 = 7α hydroxy-4-cholesten-3-one; CLDQ = Chronic Liver Disease Questionnaire; ELF = enhanced liver fibrosis; ET = Early Termination; EOS = End of study; EOT = End of Treatment; ; FGF-19 = fibroblast growth factor-19; HA = hyaluronic acid; HCV = Hepatitis C virus; IP = Investigational Product; P3NP = procollagen 3 N-terminal peptide; PBC = primary biliary cirrhosis; PK = pharmacokinetics; TE = transient elastography; wk(s) = week(s), TIMP-1 = tissue inhibitor of metalloproteinase ; VAS = Visual Analogue Scale.

^a Visit schedule should be based on Day 1. Day 1 visit must occur at least 2 weeks after screening visit.

^b Patients should be contacted by telephone/email every 3 weeks (±1 week) between clinic visits starting at Week 9 and continuing to Week 48 to assess for AEs, concomitant medications, medical/surgical procedures, and verify that s/he is dosing as directed. (see [Section 9.7.8](#)).

^c Preferably, the patient comes in to the clinic for this visit. Alternatively, site will telephone the patient for assessments and a home health nurse will visit to draw safety labs.

^d Visit should occur 3, 4, or 5 days after taking the Week 6 dose.

- ^e The patient should be instructed to fast overnight (at least 8 hours) prior to each visit. Fasting is required prior to all study visits, including screening, but water is permitted.
- ^f Height and assessment of smoking and alcohol consumption history and current habits will be assessed at Screening and Week 48. Assessment of smoking and alcohol consumption history and current habits will be assessed quarterly after Week 48.
- ^g Child-Pugh Score will be calculated based on ascites assessment, hepatic encephalopathy grade, and central laboratory evaluations per the Child-Pugh scoring system noted in the eCRF.
- ^h The EQ-5D-5L Quality of Life questionnaire is validated for use in multiple languages. If a validated translation is not available in the local language required for a specific study patient, the questionnaire will not be collected. The CLDQ measures change over time in patients with chronic liver disease.
- ⁱ New investigational product bottles will be dispensed if the patient is up-titrated. Unless up-titrated, patients are expected to use up each investigational product bottle before a new bottle will be dispensed. No new bottles will be dispensed if dose frequency is changed. Patients will be instructed to begin dosing on Day 1, after completing all study assessments. Patients will be instructed to take investigational product at approximately the same time of day. Patients must be instructed to swallow the tablet whole; they must not chew, divide, or crush the tablet.
- ^j Dose titration of investigational product may occur starting after the Week 12 Visit, or any study visit thereafter for patients on all dosing regimens, based on tolerability and safety laboratory tests from the previous visit. Subsequent dose titration(s) may occur no earlier than 6 weeks after the previous dose titration and will be based on tolerability.
- ^k Urine β -hCG pregnancy tests must be performed in females of childbearing potential prior to entry and at every visit (except Week 3). If positive, a confirmatory blood test must be performed at the central laboratory. If the confirmatory blood test is also positive, the patient may not continue in the study. (Additional testing may be conducted where required, regionally).
- ^l MELD values will be calculated based on serum chemistry and coagulation values at each visit.
- ^m The patient will be given the option to return to the clinic the following morning for the 24-hour postdose PK sample or samples can be obtained by a home health care designee. Patients who are discontinued from investigational product prior to completion of the study are encouraged to continue to follow the regular visit schedule, with the exception of PK sampling.
- ⁿ The noninvasive radiological liver fibrosis measurement devices (such as, FibroScan[®] device [Echosens; Paris, France]) will be used at all study sites to collect hepatic stiffness measurements.
- ^o Patients will complete a TE/ELF and ultrasound assessment, every 6 months (± 2 weeks) after Week 48.
- ^p ECG and urinalysis will be done yearly (± 2 weeks) after Week 48 Visit.
- ^q Ultrasound will be conducted to enhance HCC surveillance. For all on study (eg, post-Day 1) ultrasounds: Unless HCC has already been confirmed by biopsy, a second confirmatory image (eg, MRI) should be obtained to confirm suspected HCC.
- ^r If an ultrasound has been done within 12 months of Screening, and a report/adequate data are available, a pretreatment ultrasound at Screening is not required.
- ^s If ultrasound for gallbladder assessment was not performed at Screening and the historic ultrasound is >12 months from Day 1, perform ultrasound.

7.1.3. Study Duration

Patients will receive double-blind treatment for at least 48 weeks. Patients who have completed their 48-week, double-blind treatment period will continue double-blind treatment until all randomized patients have completed their 48-week treatment period and the database for that period is locked (approximately 3 years). An open-label extension study in which all patients receive OCA will be considered following review of blinded safety and PK data.

7.2. Number of Patients

Approximately 50 patients will be enrolled in this study.

7.3. Planned Dosing Regimen

All patients will initiate investigational product once weekly with OCA 5 mg or matching placebo (Table 2). Titration may be considered as early as the Week 12 Visit. Following visit procedures at Week 12, if the investigational product is tolerated and laboratory assessments do not indicate a safety concern, the patient may up-titrate to OCA 5 mg twice weekly and may start the higher dose regimen no earlier than 2 days after they took their last dose. Dosing will then occur at least 3 days apart. Every 6 weeks thereafter, based on tolerability assessments, patients can be considered for further up titration as described below (Table 2). At each titration visit, the patient may start the higher dose regimen no earlier than 2 days after the prior dose.

Patients may titrate to a maximum dose of OCA 10 mg twice weekly at least 3 days apart.

Table 2: Planned OCA or Matching Placebo Dosing Regimen

	Child-Pugh B and Child-Pugh C (Moderate and Severe Hepatic Impairment)	
	Treatment Group	
	OCA	Placebo
Starting Dose (Day 1)	5 mg once weekly	matching placebo once weekly
Titration 1 ^a	5 mg twice weekly ^b	matching placebo twice weekly ^b
Titration 2 ^a	10 mg twice weekly ^b	matching placebo twice weekly ^b

^a Planned titration regimen is shown; however, the titration of dose and/or frequency is dependent on patient tolerability.

^b Dosing per the twice weekly schedule must be at least 3 days apart.

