7.5. Dose Titration Criteria

Dose titration may follow the scheduled dosing regimens described in Section 7.3 or occur due to tolerability concerns.

Dose titrations may involve increases or decreases in dosing frequency and are dependent on tolerability (as assessed by a review of AEs and safety laboratory results). In general, down-titration may be done in response to tolerability concerns and can occur at any time.

Up-titration will be done per protocol based on tolerability, as assessed by the Investigator based on response, or following resolution of a tolerability concern that previously led to down-titration. Up-titrations may only occur to the maximum dose and frequency indicated as defined in [Section 7.3](#).

Scheduled Dose Titration - After initiation of OCA or matching placebo, titration may be considered as early as the Week 12 Visit. Subsequent titrations in dose for patients may occur no earlier than 6 weeks following an up-titration.

Tolerability Dose Titration - Investigators may decrease the dosing frequency or dose as considered clinically appropriate (eg, tolerability).

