7.5.1. Pre-Titration Tolerability Assessment Requirements

Tolerability of investigational product must be assessed prior to titrating a patient to a higher dose. To determine if a patient is eligible for a dose titration refer to [Section 7.3](#).

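### When the two titrations fall at consecutive visits, 10 mg twice weekly may start before any laboratory result on 5 mg twice weekly has been reviewed

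*Protocol*

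**What the plan says.** Protocol Section 7.3 (Table 2) sets three regimens: 5 mg once weekly, 5 mg twice weekly (Titration 1) and 10 mg twice weekly (Titration 2). The Week 12 step is allowed "if the investigational product is tolerated and laboratory assessments do not indicate a safety concern". For later steps the text reads "Every 6 weeks thereafter, based on tolerability assessments, patients can be considered for further up titration as described below". The rule for when the new regimen begins is "At each titration visit, the patient may start the higher dose regimen no earlier than 2 days after the prior dose".

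Section 7.5 makes titrations "dependent on tolerability (as assessed by a review of AEs and safety laboratory results"). Section 7.5.1 adds "Tolerability of investigational product must be assessed prior to titrating a patient to a higher dose" and refers back to Section 7.3 for eligibility.

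The question of which draw is to be reviewed is addressed in two places, and they differ:

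- Table 1, footnote j (Section 7.1.2). Its first sentence covers Week 12 and any later visit, for all regimens, with titration "based on tolerability and safety laboratory tests from the previous visit". Its second sentence reads "Subsequent dose titration(s) may occur no earlier than 6 weeks after the previous dose titration and will be based on tolerability" and names no draw.
- The note to Figure 1 (Section 7.1.1), repeated in the synopsis. It carries the same previous-visit wording but opens "Initial dose titration of investigational product may be considered as early as the Week 12 Visit", which limits the rule to the first step.

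**The concern.** A previous-visit rule suits Titration 1: at Week 12 the previous sample is Week 6, taken on the regimen whose tolerability is being judged. It does not suit Titration 2 when that step comes at the very next visit, because the previous sample then predates the first dose of 5 mg twice weekly. The step being authorised doubles the weekly dose in Child-Pugh B and C patients, for whom Section 5.5 cites raised risk of decompensation and possibly higher hepatic exposure. Bilirubin, ALT, AST and INR on the intermediate regimen are the results that bear on the decision, and no sentence makes the increase wait for them.

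**Working it through.** **Dose.** From Table 2, weekly dose is 5 × 1 = 5 mg, then 5 × 2 = 10 mg, then 10 × 2 = 20 mg.

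**Draws.** Table 1 schedules safety bloods at Screening, Day 1, Weeks 3, 6, 12, 18, 24, 30, 36, 42 and 48, then every 3 months. Contacts between visits are by telephone or email, without bloods. Titration is assessed at Weeks 12, 18, 24, 30, 36, 42 and 48: 7 visits, so 6 consecutive pairs, each 6 × 7 = 42 days apart on nominal dates. Scheduled draws strictly between paired visits: 0.

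**Trace for Weeks 12 and 18.**

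| Sample | Regimen when drawn | Role at Week 18 |
|---|---|---|
| Week 12 | 5 mg once weekly | the previous visit's result |
| Week 18 | 5 mg twice weekly | drawn that day, result pending |

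Section 9.1 requires assessments to be completed before a dose given at the site, so the Week 18 sample does reflect 5 mg twice weekly. It is the only scheduled sample that does.

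**Both readings.** If footnote j's first sentence governs Titration 2, it points to the Week 12 sample, which is on the wrong regimen. If the Figure 1 and synopsis notes govern, Titration 2 rests on tolerability including laboratory review, with no draw named, and reviewing the Week 12 result complies. Neither reading requires a result on 5 mg twice weekly. If Titration 2 comes one or more visits later, the previous-visit sample is on 5 mg twice weekly and the gap disappears.

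**Does the calendar allow it?** The minimum between titrations is 6 weeks, or 42 days.

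- Nominal dates: 42 days, allowed. Counted from start to start, Titration 1 starts on day 84 + 2 = 86 and Titration 2 on day 126 + 2 = 128 or 126 + 3 = 129, giving 42 or 43 days, also allowed.
- With ±7-day windows: 15 × 15 = 225 day combinations, of which (225 + 15)/2 = 120 reach 42 days. This counts combinations; it is not a probability.
- Quarterly visits (91 days, ±14 at each): 91 ± 28 = 63 to 119 days, always allowed. Week 48 to the first quarterly visit: 91 ± 21 = 70 to 112 days, always allowed.

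**Time from draw to first 10 mg dose.** At Weeks 18, 24, 30 and 48 serial PK includes a clinic dose, so the earliest start is 2 days later, or 3 if twice-weekly spacing applies. At Week 42 (clinic attendance, not the home-nurse route) and at quarterly visits, a same-day start is possible if the last dose was at least 2 days earlier. Week 36 is unclear: Section 12.1 implies a clinic dose, while the instructions in Sections 9.7.9 and 9.7.10 mention clinic dosing only at Weeks 18, 24 and 30.

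**Doses taken while the result is pending.** Turnaround T is not stated, so T = 1 to 5 days is assumed. Doses fall on days s, s + 3 and s + 7 for a start on day s; those before day T are counted.

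| Start day s | T=1 | T=2 | T=3 | T=4 | T=5 |
|---|---|---|---|---|---|
| 0 | 1 | 1 | 1 | 2 | 2 |
| 2 | 0 | 0 | 1 | 1 | 1 |
| 3 | 0 | 0 | 0 | 1 | 1 |

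**What happens when the result arrives.** Table 3 then applies, but its criteria are not the no-safety-concern test of the Week 12 step. Under Part B, a bilirubin rise of 1.0 mg/dL (baseline above ULN) or 1.5 mg/dL (baseline at or below ULN), or an INR rise above 0.3, without symptoms, calls for close monitoring, with interruption only if values keep rising. Under Part A, ALT or AST at 2 times baseline or more calls for a repeat in 2 to 3 days before interruption. A result that might have held back the increase need not reverse it.

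**The case against.** The strongest reply is that laboratory review before Titration 2 is already mandatory. Section 7.5 builds it into tolerability, Section 7.5.1 requires tolerability to be assessed before any increase, and footnote j names the previous visit's tests for any later visit and all regimens. That stands, and it rules out a stronger reading that a reader might infer from Section 7.3 alone: that the second step needs no laboratory review, or that no passage identifies a result. The documents do not support either. The fault is that the named result can predate the regimen being judged, and that footnote j disagrees with the Figure 1 and synopsis notes on whether the rule covers Titration 2.

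It is also fair that nothing obliges an investigator to take the fastest path. Titration may be considered, the 6-week and 2-day figures are minimums, and an unscheduled test is possible under Section 9.7.14. Child-Pugh and MELD review (Section 7.4), the triggers in Section 7.4.2, three-weekly contacts, down-titration at any time and roughly quarterly DMC meetings all reduce the consequence. They limit harm, but none makes the start of 10 mg wait for a result on 5 mg twice weekly.

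**Conclusion.** The point holds in a narrow form. At consecutive titration visits, the text permits 10 mg twice weekly to start with laboratory review resting on a sample from 5 mg once weekly. The exposure is limited to doses taken while the visit's own result is pending: 0 to 1 dose after a 2- or 3-day start and 1 to 2 after a same-day start, if turnaround is 1 to 5 days. Because turnaround and investigator behaviour are not stated, how often this would occur cannot be computed, and the calendar counts should not be read as a risk. This is a short, bounded gap in a dosing rule for a vulnerable population, worth closing because closing it is cheap.

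**What to change.** In Section 7.5.1, with Section 7.3, footnote j and the Figure 1 and synopsis notes aligned, state that 10 mg twice weekly may start only after at least one safety laboratory result drawn on 5 mg twice weekly has been reviewed and shows no safety concern. At consecutive visits this means the titration visit's own draw. Leave Titration 1 unchanged, since its previous-visit sample (Week 6 for a Week 12 titration) is already on the current regimen.

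No new sample or visit is needed, because chemistry, hematology and coagulation are already drawn at every titration visit. At consecutive visits the start is delayed by a few days and the site makes a documented telephone call to confirm it. If the 10 mg bottle is dispensed at the visit, the patient briefly holds two strengths, so the site should instruct the patient to stay on the current tablets until called.

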7.4. Monitoring and Management of Potential Hepatic Injury and/or Disease Progression

Given the chronic nature of PBC, it is important to monitor for potential hepatic injury, disease progression and/or hepatic decompensation. Child-Pugh and MELD scores will be reviewed at each visit where labs are drawn (Table 1). In addition, adverse events, signs and symptoms of potential hepatic injury or decompensation, and laboratory values will also be reviewed at regular intervals as described in Section 7.1.2. Based on biochemical and clinical assessments, the investigational product may be interrupted or discontinued per criteria discussed in

Section 7.4.2 and [Section 7.4.3](#), and close monitoring procedures will be implemented (refer to [Section 7.6](#)).

7.4.1. Signs and Symptoms of Potential Hepatic Injury or Decompensation

Patients should be instructed to contact study personnel if they notice any of the following signs and symptoms or have healthcare interactions outside of the study setting

Signs and Symptoms of Hepatic Injury or Decompensation:

- Specific signs and symptoms of liver impairment: yellowing of the skin or the whites of eyes, pale-colored stools, urine color change from pale to deep amber [dark] (reflecting impaired bilirubin metabolism)
- More general signs and symptoms of ascites and encephalopathy: confusion, swelling of the legs or abdomen
- Non-specific signs and symptoms of impaired health: nausea, vomiting, abdominal pain, diarrhea, weight loss, fever and chills, worsening or new fatigue, weakness, loss of appetite
- Significant intercurrent illnesses such as gastroenteritis may exacerbate hepatic injury or decompensation (eg, established severe abdominal pain, vomiting, and diarrhea for more than 4 days) and should be an indication for prompt investigational product interruption and complete patient evaluation

Other Symptoms:

- Worsening of renal function or likely dehydration

Healthcare Provider (HCP) Interactions:

- Visits to primary HCP or referral to any specialist for any new symptoms (other than ongoing care for stable comorbidities)
- New medications or changes to current medications prescribed from HCP or any new over the counter medications or herbal supplements
- Laboratory procedures or assessments performed by an HCP

Signs and symptoms for potential hepatic injury or decompensation should be followed by (1) evaluation of liver biochemistry for suspected drug-induced liver injury (DILI) or potential hepatic decompensation ([Section 7.4.2](#)), (2) assessment of clinical events for potential hepatic decompensation ([Section 7.4.3](#)), (3) triggering of close monitoring or investigational product interruption/discontinuation per criteria ([Section 8.4](#)), (4) documentation in the AE eCRF or the SAE eCRFs ([Section 13.1](#)), and (5) contact with the Medical Monitor.

